10. OTHER ANALYSES

10.1 Inflammatory Biomarkers

The observed value and the change in inflammatory biomarkers (e.g., interleukin-6, interleukin-8, and granulocyte macrophage-colony stimulating factor) from pre-dose to the end of the Double-blind Treatment Period (Week 12) will be presented by treatment group. Univariate and multivariate analyses of the change in inflammatory biomarkers will be described in an analysis plan, separate from this document.

10.2 Incidence of Infections Related to Uremic Pruritus

Incidence of infections related to uremic pruritus occurring during the Double-blind Treatment Period based on adverse events, hospitalizations, and/or use of antibiotics for treatment of infection related to uremic pruritus will be reported with counts and percentages for each treatment group. These will be compared using Fisher's Exact Test.

10.3 Erythropoiesis stimulating Agents and Iron

All ESA and iron usage will be presented in listings.

A thorough analysis will be performed on these outcomes and described in a separate document.

10.4 Hospitalizations, Emergency Department Encounters

The proportion of subjects who had in-patient hospitalization, and the count and percentage for whether dialysis was performed during hospitalization, and summary statistics for duration of stay will be reported by treatment for each study period.

10.5 ShOWS and OOWS

Short Opiate Withdrawal Scale

SOWS-Gossop (or ShOWS) is a self-administered scale for grading opioid withdrawal symptoms over a 24-hour period. This subject-rated scale consists of 10 items, scored from 0 (none) to 3 (severe); the total score is calculated as the sum of the individual items (total score range 0–30). If any individual values are missing, the total will be missing. The higher the score, the greater the severity of associated withdrawal.

The ShOWS will be presented as a paper worksheet to be filled by each subject, at home on non-dialysis days and at the dialysis unit on dialysis days, at a similar time of the day for a given subject during the 2-week Discontinuation Period (during which no study drug will be administered).

Objective Opiate Withdrawal Scale

The OOWS-Handelsman contains 13 physically observable signs, rated present (score of 1) or absent (score of 0); the total score is calculated as the sum of the individual items (total score range 0–13), based on a timed period of 5 to 10 minutes of observation of the subjects by a rater. If any individual values are missing, the total will be missing. Higher total scores will indicate more severe withdrawal signs. The rater will be a qualified staff member who will be trained by the Sponsor.

The OOWS will be presented as a paper worksheet to be filled by a qualified staff member at the dialysis unit on dialysis days (Discontinuation days 1,3,5,8,10 and 12), at similar time of the day for a given subject during the 2-week Discontinuation Period (during which no study drug will be administered).

Analyses

Summary statistics for the daily ShOWs and the OOWS collected at each dialysis visit, including number of non-missing observations, mean, standard deviation, median, minimum, and maximum of ShOWs and OOWS, will be tabulated by treatment group for the Double-blind Discontinuation Safety Population and Double-blind Discontinuation Population. Figures for the overall mean scores over time will also be presented. The ShOWS scores on Discontinuation Period Days 2, 3, 4, 5, 6, and average assessment on days after Day 6 will be analyzed to compare the treatment groups at each visit, using an ANCOVA model, with treatment group and baseline (Day 85) value as a covariate.

[figure not shown]
The OOWS scores will be analyzed using a similar ANCOVA model at each day of collection (Discontinuation days 1,3,5,8,10 and 12). Summary statistics will be reported for all collection time points and the average of the days after Day 6 (that is, Days 8, 10 and 12); the ANCOVA model will only be performed for the visits described above.

Additionally, OOWS will be summarized by the number and percentage of subjects who have a score = 2; number and percentage of subjects who have a score = 3; number and percent of subjects who have a score = 4; and the number and percentage of subjects who have a score >4. This will be reported by day up to Discontinuation Period Day 5, and then using the maximum any time during Days 8 to 12; and then the maximum anytime during the Discontinuation Period.

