4.2.4 Pharmacokinetics in Hemodialysis Patients

CR845 is eliminated primarily through the kidney and no major metabolites have been identified in humans. Consequently, total body clearance of CR845 in patients with severe renal impairment is reduced relative to healthy, matched, control patients (CR845-CLIN1005) such that plasma levels of CR845 remain relatively constant until cleared during dialysis in hemodialysis patients (CR845-CLIN1003 and CR845-CLIN2005 [Part A]). Half-life ranges between 26 and 34 hours in hemodialysis patients compared to a typical range of 2 to 3 hours in patients with normal renal function. Thus, lower doses of CR845 can be administered at a less frequent interval in hemodialysis patients to achieve the same or higher overall exposure compared to individuals with normal renal function. Based on this pharmacokinetic profile, CR845 does not need to be administered more than 3 times a week after each hemodialysis session, which is convenient for this patient population and ensures treatment compliance in a population already burdened with complex medication schedules.

The pharmacokinetic profile of repeat-dose CR845 was studied in 24 hemodialysis patients who received doses of 0.5, 1.0, or 2.5 mcg/kg 3 times per week for 1 week (CR845-CLIN2005 [Part A]). In this study, there were dose-proportional increases in

maximum concentration and area under the curve, and minimal to no accumulation with repeat doses due to clearance of the drug by hemodialysis (see [Investigator's Brochure](#) for details).

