8.9.4 Discontinuation Period Additional Assessments

Baseline ShOWS and OOWS will be the scores collected on the dialysis day on Day 85 (Double-blind EOT/Early Termination) (Table 2). Only patients who have a baseline ShOWS and OOWS will be included in the analysis.

Summary statistics for the daily ShOWs and the OOWS collected at each dialysis visit, including number of non-missing observations, mean, standard deviation, median, minimum, and maximum median of ShOWS and OOWS will be tabulated by treatment group. Figures for the overall mean scores over time will also be presented.

The ShOWS scores on discontinuation days 1, 2, 3, and >3 will be analyzed to compare the treatment groups at each visit, using an Analysis of Covariance (ANCOVA) model, with treatment group and baseline value as a covariate. The OOWS scores will be analyzed using a similar ANCOVA model at each day of collection. In addition, between-treatment group comparisons over the overall 2-Week Discontinuation Period will be performed using an MMRM with treatment group, discontinuation day, and treatment group-by-day interaction as fixed effects, baseline value as the covariate, and patient as a random effect. An unstructured covariance matrix will be used to model the covariance of within-patient scores. These analyses will be performed based on all postbaseline scores using only the observed cases without imputation of missing values.

Exploratory analyses may be performed, depending on sample size, for the subgroup of patients who also stop taking concomitant opioid medications during the 2-week Discontinuation Period.

Adverse events (AEs) and vital signs potentially related to withdrawal that occur during the 2-week Discontinuation Period will be identified based on a blinded review of the data, and will be summarized by randomized treatment group, and compared to the 2-week period prior to discontinuation.

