3. GENERAL ANALYSIS AND REPORTING CONVENTIONS

This section discusses general policies to be employed in the analysis and reporting of the data from the study. Departures from these general policies will be described, if applicable, in the appropriate sections of this SAP. When this situation occurs, the rules set forth in the specific section take precedence over the general policies.

For categorical variables, summary statistics will consist of the number and percentage of subjects in each category. All percentages will be rounded to one decimal point. The number and percentage of subjects will always be presented in the form XX (XX.X%) where the percentage is in parentheses. To ensure completeness, all summaries for categorical and discrete variables will include all categories, even if none of the subjects had a response in a particular category. Denominators for each analysis will be based on the population of interest (e.g., safety population; subjects with non-missing data).

For continuous variables, summary statistics will consist of the number of subjects with data, mean, median, standard deviation, minimum, and maximum values. The summary statistic n will be the number of subjects with non-missing values. All means and medians will be reported to one more significant digit than the values being analyzed. Standard errors and standard deviations will be reported to two more significant digits than the values being analyzed. The minimum and maximum will be reported to the same number of significant digits as the values being analyzed.

For tests of hypothesis of treatment group differences, the associated p-value will be reported. All p-values will be rounded to three decimal places; p-values that round to 0.000 will be presented as “<0.001”. P-values are descriptive for outcomes and analyses not included in the multiplicity algorithm.

In general, the baseline value will be considered the last non-missing measurement observed prior to the first dose of study treatment; the NRS will use the mean of the Run-in Period. The opiate withdrawal scales will use the Day 85 assessment as baseline.

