12. CHANGES TO THE ANALYSES PLANNED IN THE PROTOCOL

- The protocol defines clinically notable vital signs based on values observed at the visit and on change from baseline. The definition was updated to remove the criteria based on change from baseline since it was deemed not necessary.
- The protocol states that Akaike information criterion will be used to select the appropriate covariance matrix structure for the MMRM analysis. The SAP uses an unstructured covariance matrix structure as the first choice. Should the model fail to converge, a compound symmetric covariance matrix will be used instead.
- Throughout the protocol, MMRM analyses state that random subject effects will be used, but also provide R-side matrix structures, rendering the random effect (GZ matrix) unnecessary. Random effects have therefore been removed throughout.
- The protocol states that the ShOWS scores on Discontinuation Period Days 1, 2, and 3 and days after Day 3 will be compared between treatment groups using an ANCOVA model. Because scores taken on Day 1 of this period will be included in the model as the subject's baseline score, this analysis was revised to compare ShOWS scores on Discontinuation Period Days 2, 3, and 4, 5, 6 and average assessment on days after Day 6. Additionally, the MMRM analysis was dropped, a categorical analysis was added for OOWS, and text clarifying the OOWS collection times was added.
- The protocol states that adverse events and vital signs potentially related to withdrawal that occur during the 2-week Discontinuation Period will be compared to the adverse events and vital signs reported during the 2-week period preceding the Discontinuation Period. Per the SAP, no comparison to the 2-week period prior to the Discontinuation Period will be made.
- The rules of mapping the early termination visit and the unscheduled visits into a scheduled visit based on visit windows were clarified in the SAP. The protocol states that if 2 or more evaluations occur in the same visit window, the evaluation closest to the target visit day will be selected for inclusion in the analysis. This was revised to select the non-missing value in the order of scheduled visit, early termination visit, and the unscheduled visits.
- The Double blind Discontinuation and Double blind Discontinuation Safety Populations were added.

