DP = Discontinuation Period; EOT = end of treatment; ESA = erythropoiesis-stimulating agent; F = Friday; IV = intravenous; M = Monday; NRS = numerical rating scale; OOWS = Objective Opiate Withdrawal Scale; PRO = patient-reported outcome; Sa = Saturday; ShOWS = Short Opiate Withdrawal Scale; Th = Thursday; Tu = Tuesday; W = Wednesday

- a. Each visit during the Double-blind Treatment Period will coincide with the patient's normal dialysis treatments.
- b. The End-of-Treatment Visit in the Double-blind Treatment Period corresponds to Day 1 of the Discontinuation Period.
- c. Medical history will be updated on Day 1 with any changes since the Screening Visit, and inclusion/exclusion criteria will be confirmed prior to randomization.
- d. Electrocardiogram must be performed at screening, and Day 85 prior to the start of dialysis.
- e. Vital signs, including body temperature, heart rate, and blood pressure, will be obtained at the specified visits when the patient is in a sitting or semi-recumbent position prior to the start of dialysis. Heart rate will be collected at each dialysis; if clinically significant and outside the prespecified visits per SOE, the heart rate will be recorded on the relevant CRF page.
- f. Pre-dialysis vital signs will be recorded on Days 1, 15, 29, 43, 57, and 85 only.
- g. Vital signs, including body temperature, heart rate, and blood pressure, will be obtained prior to the start of each dialysis at each dialysis visit during the Discontinuation Period.
- h. Blood samples for clinical laboratory evaluation will be taken on Days 1 and 85 only.
- j. Training on Worst Itching Intensity NRS on the first day of the Run-in Period.
- k. Training on Skindex-10 Scale and 5-D Itch Scale may be performed at any time during the week prior to randomization or on Day 1 of the Double-blind Treatment Period.
- l. Patients will be requested to complete their worksheets each day at a similar time (either at home on non-dialysis days around the normal start time of their dialysis or in the dialysis unit). On dialysis days, the worksheets will be completed prior to or during dialysis, but must be completed prior to dosing of the study drug. During Discontinuation Period, worksheets to be completed on dialysis days only.

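### The OOWS ANCOVA is specified on Discontinuation Day 1, where the outcome is its own baseline covariate, so no treatment effect can be estimated there

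*SAP*

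**What the plan says.** **The model.** SAP Section 10.5 analyses ShOWS "using an ANCOVA model, with treatment group and baseline (Day 85) value as a covariate". For OOWS it continues: "The OOWS scores will be analyzed using a similar ANCOVA model at each day of collection (Discontinuation days 1,3,5,8,10 and 12", where the list ends. It adds that "the ANCOVA model will only be performed for the visits described above", so the list is the operative one and Day 1 is on it.

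**The baseline.** SAP Section 3: "The opiate withdrawal scales will use the Day 85 assessment as baseline". Protocol Section 8.9.4 agrees: "Baseline ShOWS and OOWS will be the scores collected on the dialysis day on Day 85".

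**The visit.** SAP Appendix 16.1, footnote b: "The End-of-Treatment Visit in the Double-blind Treatment Period corresponds to Day 1 of the Discontinuation Period". Footnote b of Protocol Table 2 says the same and places that visit on Day 85.

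**What the SAP changed.** Section 12 gives its reason for revising the ShOWS analysis: "Because scores taken on Day 1 of this period will be included in the model" as the baseline score. The ShOWS comparison therefore moves to Days 2 to 6 and an average of later days. For OOWS, Section 12 records only a categorical summary and clarified collection times. It also drops the MMRM for these scales.

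**Which text governs.** Protocol Section 8.9.4 limited these analyses to scores after baseline. The SAP does not repeat that limit, names Day 1, and states in Section 1 that it prevails over the protocol.

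**The concern.** An ANCOVA whose outcome is also its covariate cannot estimate anything. The Discontinuation Period is there to look for physical dependence, and with the MMRM gone the by-day ANCOVA is the only between-arm model left for the two scales. At Day 85, the first OOWS assessment, that model returns no information. The SAP's authors saw the problem for ShOWS and did not carry the correction across.

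A second, weaker question concerns the later days. For a completer, Day 85 falls 3 days after the last scheduled dose, and no ShOWS or OOWS score is scheduled before it. If some withdrawal effect were already present at that visit, adjusting for the Day 85 score would take part of it out of the later-day contrasts.

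**Working it through.** The documents give no power or sample size for these scales, so there is no stated figure to reproduce.

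**1. Is Day 1 really Day 85?** With Discontinuation Day k = Day 84 + k, the listed days 1, 3, 5, 8, 10 and 12 are Days 85, 87, 89, 92, 94 and 96. These continue the three-times-weekly pattern (Days 78, 80, 82, then 85). If Day 1 were Day 86, the list would fall on Days 86, 88, 90, 93, 95 and 97, which are not dialysis days on that schedule, and OOWS is collected only at dialysis. Day 1 is Day 85.

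**2. The Day 1 model.** Write Y = b0 + b1·T + b2·B + error, with T the arm and B the Day 85 score. On Day 1, Y = B for every patient. The solution b0 = 0, b1 = 0, b2 = 1 fits exactly, and is unique if scores vary within an arm. The residual sum of squares is 0, so the standard error of b1 is 0 and the test statistic is 0/0.

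Numerical check with 175 per arm and simulated counts having a real difference:

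| Quantity | Result |
|---|---|
| Raw difference between arms | 1.06 points |
| Fitted treatment effect | -1.9 × 10^-15 |
| Its printed standard error | 2.4 × 10^-16 |
| Residual sum of squares | 1.4 × 10^-27 |
| R-squared | 1 |

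The ratio of the second line to the third is about -7.8, but it is one rounding error divided by another and means nothing.

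**3. Drug status at Day 85.** The last scheduled dose is Day 82, and 85 - 82 = 3 days, or about 72 hours. Protocol Section 4.2.4 says: "Half-life ranges between 26 and 34 hours in hemodialysis patients compared to a typical range of 2 to 3 hours". On those half-lives the fraction left is 2^(-72/26) = 0.147 to 2^(-72/34) = 0.230. The same section also says plasma levels hold roughly steady until dialysis removes the drug, and SAP Section 8.2.4.3 says the week's last dose stays until the next week's first dialysis. Losing 77 to 85% beforehand does not fit those two statements.

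**4. Later days.** Let d be the true later-day effect in SD units, f the share of it already present at Day 85, and rho the correlation between the Day 85 and later scores (equal SDs). Then:

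- adjusted effect = d(1 - rho·f)
- SE = sqrt[(2/n)(1 - rho²)(1 + (d·f)²/4)]

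The values of d, rho and f are assumptions; the documents give none. I take d = 0.35, n = 175 per arm (the planned size, with no attrition) and rho = 0.3 to 0.7. Unadjusted power is 90.6%.

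| f | Share of effect kept | Power with adjustment |
|---|---|---|
| 0 | 100% | 92.9 to 99.6% |
| 0.5 | 65 to 85% | 80.6 to 84.3% |
| 1 | 30 to 70% | 27.3 to 65.8% |

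Worked case, rho = 0.5 and f = 1: the effect is 0.35 × 0.5 = 0.175; SE = sqrt(0.01143 × 0.75 × 1.0306) = 0.0940; 0.175/0.0940 - 1.96 = -0.098; power 46.1%. Simulation (4,000 runs) gave 45.9%. With 140 per arm, unadjusted power is 83.4% and the f = 1 range is 22.7 to 56.2%.

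**The case against.** The best defence of the Day 1 listing is that it is a slip: the collection days were copied into the ANCOVA sentence, the protocol's limit to scores after baseline would have excluded Day 1, and the model would fail visibly when run. That is probably how it arose, but it does not cure the text. The SAP's explicit list prevails.

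Several points on the other side do stand:

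- A reader might infer that Day 1 would be reported as no difference between arms. The documents do not support that: a model with no residual variance yields no valid p-value, null or otherwise.
- The Day 1 data are not lost. OOWS is summarised by arm at every collection point, and counts of scores 2, 3, 4 and above 4 are given by day up to Day 5, with no baseline covariate. The screen for withdrawal-type adverse events in SAP Section 9.2 runs from the last dose, not from Day 85.
- A reader might also infer that the later-day comparisons are biased toward finding no dependence. That requires withdrawal to have begun by Day 85, which nothing in the documents establishes. The scales are completed early in the Day 85 dialysis session and doses are given after dialysis, so no scheduled dose has yet been missed. The gap from Day 82 to Day 85 is the ordinary weekend gap, as from Day 5 to 8 or Day 12 to 15. If drug does persist until that dialysis, Day 85 is close to an on-drug baseline and adjusting for it helps.
- A percentage of drug remaining is not a measure of bias on either scale.
- The 3-day interval holds for completers on the regular schedule. It need not hold for early terminators.

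**Conclusion.** The Day 1 OOWS ANCOVA is wrong as written. That follows from the SAP's own text and needs no assumption. One of six planned OOWS models cannot be estimated; the other five can.

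The later-day question is a conditional caution, not an error. Adjustment keeps a fraction 1 - rho·f of the effect. If f = 0 nothing is lost and precision improves; if f is above 0 the contrast is attenuated. Complete removal needs rho·f = 1, which is the Day 1 case. The Day 85 baseline was prespecified in the protocol and is a defensible end-of-treatment reference. What the documents do leave open is the drug's status at that visit, because the steady-until-dialysis statements and the half-life point in different directions.

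SAP Section 3 makes p-values outside the multiplicity procedure descriptive, so no confirmatory conclusion is affected.

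**What to change.** 1. In SAP Section 10.5, delete Day 1 from the OOWS ANCOVA list and keep Days 3, 5, 8, 10 and 12. Record the change in Section 12 beside the ShOWS one.
2. Compare Day 85 OOWS and ShOWS between arms without a baseline covariate.
3. Optionally, show the later-day comparisons without the Day 85 covariate beside the ANCOVA, labelled as a sensitivity analysis.
4. Reconcile the statements on drug persistence until dialysis (SAP Section 8.2.4.3, Protocol Section 4.2.4) with the half-life given in Protocol Section 4.2.4.

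The cost is SAP wording and a few table rows; no new data are needed. There are two downsides. Later-day comparisons without the covariate are less precise when Day 85 carries no withdrawal effect: in the illustration, 90.6% power against 92.9 to 99.6%. And both discontinuation populations (SAP Sections 4.4 and 4.5) are defined by events after randomization: one requires a discontinuation visit, the other also 12 completed weeks and at least 6 doses in the last 2 weeks. Comparisons within them are not fully protected by randomization, and the report should say so.

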Record dose of ESA and IV iron	X		Record on an ongoing basis						X		
Record number of missed dialysis visits and reason(s)			Record on an ongoing basis								
IV administration of study drug			Record on an ongoing basis								
Inflammatory biomarker samples ^o			X						X		
Adverse event monitoring	X	X	Record on an ongoing basis						X	X	
Concomitant medications (including antipruritic medications) ^p			X	Record on an ongoing basis						X	X
Structured Safety Evaluation ^f		X		X			X			X	

DP = Discontinuation Period; ESA = erythropoiesis-stimulating agent; F = Friday; IV = intravenous; M = Monday; NRS = numerical rating scale; OOWS = Objective Opiate Withdrawal Scale; PRO = patient-reported outcome; Sa = Saturday; ShOWS = Short Opiate Withdrawal Scale; Th = Thursday; Tu = Tuesday; W = Wednesday

-
- a. Each visit during the Double-blind Treatment Period will coincide with the patient's normal dialysis treatments.
 - b. The End-of-Treatment Visit in the Double-blind Phase will be the first dialysis visit following the last dose of study drug (ie, first dialysis on Week 13 [Day 85]), which also corresponds to Day 1 of the Discontinuation Period (DP Day 1).
 - c. Medical history will be updated on Day 1 with any changes since the Screening Visit, and inclusion/exclusion criteria will be confirmed prior to randomization. Antipruritic medication will be updated at each dialysis visit during the Run-in Period.
 - d. Electrocardiogram must be performed prior to the start of dialysis at screening, Day 85 (End of Treatment), or at Early Termination visit.
 - e. Pre-dialysis vital signs, including body temperature, heart rate, and blood pressure, will be recorded on Days 1, 15, 29, 43, 57, 71 and 85 (End of Treatment), or at Early Termination visit only when the patient is in a sitting or semi-recumbent position. Heart rate will be measured at each dialysis; if heart rate is clinically significant and outside the prespecified visits per Schedule of Events, the heart rate will be recorded on the relevant CRF page.
 - f. Pre-dialysis vital signs, including body temperature, heart rate, and blood pressure, will be recorded at each dialysis visit during the Discontinuation Period. Heart rate will be measured at each dialysis.
 - g. Blood samples for clinical laboratory evaluation will be taken at screening, and on Days 1 and 85 (End of Treatment), or at Early Termination visit only.

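### The OOWS whole-period maximum includes Discontinuation Day 1, the plan's own baseline, so a score present only at baseline is reported as reached during the Discontinuation Period

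*SAP*

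**What the plan says.** SAP 10.5 adds a categorical OOWS summary that the protocol does not contain. It counts subjects scoring 2, 3, 4 or more than 4, by day to Discontinuation Day 5, "and then using the maximum any time during Days 8 to 12; and then the maximum anytime during the Discontinuation Period". The same section has the scale completed on "dialysis days (Discontinuation days 1,3,5,8,10 and 12), at similar time of the day for a given subject during the 2-week Discontinuation Period".

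The first of those days is the baseline visit:

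- SAP 3: "The opiate withdrawal scales will use the Day 85 assessment as baseline".
- Protocol 8.9.4: "Baseline ShOWS and OOWS will be the scores collected on the dialysis day on Day 85 (Double-blind EOT/Early Termination").
- SAP 16.1, footnote b: "The End-of-Treatment Visit in the Double-blind Treatment Period corresponds to Day 1 of the Discontinuation Period".
- Protocol 6.5.1, Table 2, footnote b, describes the end-of-treatment visit as the "first dialysis on Week 13 [Day 85]), which also corresponds to Day 1 of the Discontinuation Period (DP Day 1").

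Neither the overall maximum nor any general rule in the SAP limits it to post-baseline visits.

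**The concern.** The table is meant to show how many subjects reached a given score once study drug had stopped, and SAP 10.5 reads higher OOWS totals as more severe withdrawal. A baseline score cannot show a change from baseline, yet it can set a subject's maximum by itself. A subject with 3 on Day 85 and 0 at the five later visits would be reported as a 3 for the Discontinuation Period.

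The table matters more because SAP 12 drops the protocol's repeated-measures comparison over the two weeks. For OOWS that leaves results by visit, an average and a maximum over Days 8 to 12, and this maximum. It is the only OOWS summary figure covering the whole period, in a part of the study that Protocol 7.1 says was designed to assess physical dependence.

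**Working it through.** The plan gives no figure for this table, so there is none to reproduce. There are two checks: which visit Day 1 is, and how much it can contribute.

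**Day mapping.** With Day 1 as the first dialysis of the week, the dialysis days from Day 85 are 85, 87, 89, 92, 94 and 96.

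- Study day minus 84 gives 1, 3, 5, 8, 10, 12, which is exactly the OOWS list in SAP 10.5.
- If Day 86 were Discontinuation Day 1, study day minus 85 would give 0, 2, 4, 7, 9, 11, which does not match.

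So six scores feed the overall maximum, and the first is the Day 85 baseline. The maximum over Days 8 to 12 is unaffected.

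**Size, on assumed inputs.** The documents give no OOWS rates or variability. Assume no withdrawal effect, probability p of a score of 2 or more at each visit (3%, 5%, 10%), and within-subject correlation r (0, 0.3, 0.6) in a beta-binomial model. The probability of no such score in k visits is

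- r = 0: N(k) = (1 − p)^k
- r > 0: N(k) = product over j = 0 to k − 1 of (b + j)/(a + b + j), with a = p(1 − r)/r and b = (1 − p)(1 − r)/r.

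The rule as written counts 1 − N(6). Post-baseline visits alone count 1 − N(5). The difference is the subjects who score 2 or more on Day 85 only. The share of written-rule cases already at 2 or more on Day 85 is p/(1 − N(6)).

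Example, p = 0.05 and r = 0.3: a = 0.05 × 0.7/0.3 = 0.1167 and b = 0.95 × 0.7/0.3 = 2.2167. N(5) = 0.9500 × 0.9650 × 0.9731 × 0.9781 × 0.9816 = 0.8565. N(6) = 0.8565 × 0.9841 = 0.8429. The written rule gives 15.71% and post-baseline visits give 14.35%, a difference of 1.36 points, and 1.36/15.71 = 9% of cases.

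| p | r | Six visits, as written | Five post-baseline visits | Difference (points) | Cases removed | Cases already ≥2 on Day 85 |
|---|---|---|---|---|---|---|
| 3% | 0 | 16.70% | 14.13% | 2.58 | 15% | 18% |
| 3% | 0.3 | 9.69% | 8.82% | 0.87 | 9% | 31% |
| 3% | 0.6 | 6.14% | 5.81% | 0.33 | 5% | 49% |
| 5% | 0 | 26.49% | 22.62% | 3.87 | 15% | 19% |
| 5% | 0.3 | 15.71% | 14.35% | 1.36 | 9% | 32% |
| 5% | 0.6 | 10.08% | 9.55% | 0.53 | 5% | 50% |
| 10% | 0 | 46.86% | 40.95% | 5.90 | 13% | 21% |
| 10% | 0.3 | 29.38% | 27.06% | 2.32 | 8% | 34% |
| 10% | 0.6 | 19.43% | 18.47% | 0.96 | 5% | 51% |

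The last two columns answer different questions. Most subjects at 2 or more on Day 85 score that again later, so they remain cases when Day 1 is dropped. In the example, subjects below 2 on Day 85 who later reach 2 number 15.71 − 5.00 = 10.71%. That figure can be read only from a table crossed with the Day 85 category.

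**The case against.** **Day 85 may not belong to the period.** Protocol 8.8.1 ends the treatment period at the dialysis after the last injection, SAP 2.2.1 places Day 85 at the end of treatment, and the SAP 16.1 schedule heads the Discontinuation Period column with study days 86 to 98. That is a real labelling inconsistency. It does not outweigh the two footnotes and the day list in SAP 10.5, which fits only if Day 1 is Day 85.

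**Day 85 may already carry some withdrawal.** A reader might infer that Day 85 is certainly before withdrawal. Protocol 4.2.4 is mixed: levels stay fairly constant until dialysis, but the half-life is 26 to 34 hours. If that half-life applies over about 72 hours from the Day 82 dose, 0.5^(72/26) = 15% to 0.5^(72/34) = 23% of the drug remains. SAP 9.2 also screens withdrawal events within 6 days of the last dose, which covers Day 85. So keeping Day 85 in an any-time maximum could be defended as cautious. This stands as uncertainty about pharmacology. It does not change the fact that the plan declares Day 85 the baseline.

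**The plan's other provisions do not settle it.** SAP 12 moved the ShOWS comparison off Day 1 with the words "Because scores taken on Day 1 of this period will be included in the model as the subject's baseline score". That concerns an outcome equal to its own covariate, so it cannot be cited as the same reason for changing a descriptive maximum. In Protocol 8.9.4, "These analyses will be performed based on all postbaseline scores" refers to the modelled comparisons, and the categorical table did not yet exist. Both show that the plan treats Day 1 as baseline, and no more than that.

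**It is visible and low stakes.** The by-day rows show the Day 1 distribution, there is a randomised placebo arm, and the table is descriptive and outside the testing hierarchy. All true. But separate by-day rows cannot show which subjects owe their maximum to Day 1.

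**Conclusion.** The point holds. As written, the overall OOWS maximum runs over six visits, one of which is the plan's baseline, and a score seen only there is reported as reached in the Discontinuation Period. On the assumed rates, correcting this removes about 5% to 15% of cases (0.3 to 5.9 percentage points). No efficacy result or test depends on it.

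Two stronger conclusions are tempting and are not supported. First, the 18% to 51% of cases already at 2 or more on Day 85 is not the effect of including Day 1; most of those subjects stay in the count when Day 1 is removed. Second, no dilution of a CR845–placebo difference can be quantified. The calculation contains no treatment effect, and the documents give no OOWS rates by arm. Signs common to both arms could mask a difference, while signs caused by drug still present on Day 85 could raise the CR845 arm alone.

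**What to change.** In SAP 10.5:

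1. Define the overall maximum over post-baseline OOWS visits only: Discontinuation Days 3, 5, 8, 10 and 12.
2. Keep Day 85 in the by-day rows, labelled as baseline.
3. Tabulate the post-baseline maximum against the Day 85 category, by treatment group, so that new or higher scores can be read directly. Step 1 alone does not do this: a subject with a constant score of 2 still has a post-baseline maximum of 2.
4. In the same edit, remove Day 1 from the OOWS ANCOVA days, where outcome and baseline covariate are the same score. That change alone would leave the maximum as it is, so both are needed.

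The study-day header for the Discontinuation Period in SAP 16.1 should be aligned with footnote b at the same time. The cost is a few SAP sentences and one table shell, with no new data and no loss of anything now reported about Day 85.
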